### Study title

Periimplant Mucosa Dynamics Around Divergent and Concave Atlantis™ Abutment Transition Profiles.

### Study design

*(A one-sentence summary of study design features)*

A two-arm, parallel group, randomized controlled clinical trial on adult human subjects receiving divergent or concave Atlantis™ abutments to assess peri-implant mucosa changes from prosthesis delivery to 1 year.

### Study centre(s) and number of subjects planned

*(The address where the study will be conducted, number of patients planned and if applicable distribution of patients per site)*

Craniofacial Clinical Research Center (CCRC) at The University of Iowa College of Dentistry

n= 60 subjects (30 subjects – concave abutment profile, 30 subjects – divergent abutment profile)

### Study period

*(month & year)*

- **Estimated Start date** *(first patient enrolled)* Summer 2013 to Fall 2013
- **Estimated End date** *(last patient completed follow up)* Fall 2014 to Winter 2015
- **First data available for presentation** Winter 2015

### Study objectives

- (Primary) Compare the influence of experimental concavities in the subgingival transition zone of Atlantis™ abutments on peri-implant mucosal dynamics from final restoration delivery to one year, as compared to current Atlantis™ abutments with linear divergent transition profiles.
- (Secondary) Quantify the horizontal soft tissue thickness changes around concave and divergent abutment transition profiles from final restoration delivery to one year.
- (Secondary) Evaluate changes in peri-implant health indicators, such as Gingival Index (GI), Probing Pocket Depth (PPD), and Bleeding on Probing (BOP).

### Study population

*(Short description of target population and indication studied, including relevant criteria for exclusion/inclusion)*

We propose to invite 60 patients participating in a RCT at The University of Iowa College of Dentistry, beginning early/mid 2013 on the efficacy of alveolar ridge preservation ([name] – Principle Investigator). If necessary, additional patients requiring a single-tooth implant (with the same inclusion/exclusion criteria proposed below) will be recruited.

#### Inclusion Criteria:

- 18 years of age or greater
- Subjects requiring replacement of a single-rooted tooth in the maxillary arch from first premolar to first premolar with an implant-supported restoration
- Teeth adjacent (mesial and distal) to study site must consist of two stable, natural teeth without signs of periodontal bone loss (<2.0mm) and/or significant soft tissue loss
- An opposing dentition with teeth, implants, or fixed prosthesis
- Subjects must be willing to follow instructions related to the study procedures
- Subjects must have read, understood, and signed the informed consent document

**Exclusion Criteria:**

- Insufficient interocclusal space for implant placement and/or restoration at study site
- More than 2.0mm vertical bone loss at study site as measured from the mid-buccal crest of the bone on the adjacent teeth
- Untreated rampant caries
- Tobacco use free for  $\leq$  6 months
- Liver or kidney dysfunction/failure
- Active severe infectious diseases that may affect normal healing and/or bone metabolism (e.g. AIDS)
- Uncontrolled diabetes
- Current alcohol or drug abuse
- Need for systemic corticosteroids or any other medication that would influence post-operative healing and/or osseointegration
- History of relevant head/neck cancer and/or radiation of the head/neck
- Subjects who currently use bisphosphonates or have a history of bisphosphonate use
- Subjects with metabolic bone diseases such as osteoporosis or Paget's disease of bone
- Known pregnancy or nursing mothers
- Unable or unwilling to return for follow-up visits for a period of 1 year
- Unlikely to be able to comply with study procedures according to investigators judgement

**Investigational product/comparator** (*State the devices / products that will be investigated / used and for comparative studies also the comparator/s*)

Atlantis™ Crown abutments fabricated with either divergent or concave subgingival transitional profiles supported by Dentsply Osseospeed™ PLUS implants.

**Outcome variables**

- Apico-coronal changes of the peri-implant mucosal zenith from prosthesis delivery to one year (Primary).
- Submarginal bucco-lingual soft tissue thickness in the peri-implant transition zone relative to a fixed reference point.
- Quantification of the topographical and volumetric features of the interface between the peri-implant mucosa and the transition zone.
- Keratinized mucosa width in an apicocoronal direction at the midfacial aspect of the implant site.
- Gingival Index (GI), Plaque Index (PI), Bleeding on probing (BOP) and probing pocket depths (PPD) at six sites (disto-lingual, mesio-lingual, mid-lingual, mesio-buccal, disto-buccal, mid-buccal).

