# Periimplant Mucosa Dynamics Around Dynamic and Concave AtlantisTM Abutment Transition Profiles

October 1, 2019

We removed all patients without a randomized treatment and/or without any data collection. We did keep subjects with partial data in at least one of the variables. All analyses were performed using R version 3.6.0.

Table 1: Canfield

Treatment	Mean	SD	Min	Max	Median	N
Delivery						
Concave	9.770	1.146	7.46	11.67	9.86	29
Divergent	9.860	1.148	7.42	11.90	10.06	25
1 Month						
Concave	9.618	1.160	7.05	11.52	9.79	29
Divergent	9.684	1.203	7.25	11.92	9.84	25
3 Month						
Concave	9.610	1.174	6.96	11.52	9.75	29
Divergent	9.674	1.231	7.10	11.78	9.81	25
6 Month						
Concave	9.599	1.160	7.10	11.52	9.73	29
Divergent	9.652	1.166	7.27	11.56	9.80	25
12 Month						
Concave	9.596	1.167	6.91	11.45	9.70	29
Divergent	9.622	1.258	6.89	11.54	9.80	25

Average Canfield

[figure not shown]

Table 2: Geomagic

	Mean	SD	Min	Max	Median	N
Ld (Divergent)	2.5039	0.6349	1.4212	4.1078	2.457	29
Lc (Concave)	2.6484	0.6608	1.5736	4.3982	2.539	29
Δ Linear (Lc - Ld)	0.1445	0.1361	0.0122	0.6119	0.117	29
Vd (Divergent)	165.8893	41.7412	91.9577	242.6630	165.796	29
Vc (Concave)	157.9359	41.1081	88.1219	226.8050	161.692	29
Δ Volume (Vc - Vd)	-7.9534	6.1022	-21.7929	-0.2594	-6.537	29

Table 3: Probing Depth

Surface	Treatment	Mean	SD	Min	Max	Median	N
1 Month							
MB	Concave	2.68	0.65	2	4	3	31
	Divergent	2.63	0.56	2	4	3	27
MIDB	Concave	1.5	0.5	1	2	1.5	27
	Divergent	1.82	0.66	1	3	2	22
DB	Concave	2.58	0.72	2	4	2	31
	Divergent	2.85	0.77	2	4	3	27
ML	Concave	2.81	0.7	2	4	3	31
	Divergent	2.85	0.77	1	4	3	27
MIDL	Concave	1.89	0.51	1	3	2	27
	Divergent	1.86	0.77	1	3	2	22
DL	Concave	2.84	0.78	2	5	3	31
	Divergent	2.85	0.82	1	4	3	27
Average	Concave	2.42	0.4	1.67	3.17	2.5	31
	Divergent	2.53	0.45	1.67	3.25	2.5	27
3 Months							
MB	Concave	2.68	0.6	2	4	3	31
	Divergent	2.56	0.58	2	4	3	25
MIDB	Concave	1.63	0.49	1	2	2	27
	Divergent	1.75	0.61	1	3	2	22
DB	Concave	2.58	0.67	2	4	2	31
	Divergent	2.92	0.57	2	4	3	25
ML	Concave	2.84	0.86	1	5	3	31
	Divergent	3.06	0.68	2	4	3	25
MIDL	Concave	1.85	0.77	1	3	2	27
	Divergent	2.18	0.73	1	4	2	22
DL	Concave	2.94	0.73	2	4	3	31
	Divergent	3.12	0.73	2	5	3	25

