Average	Concave	2.47	0.47	1.67	3.5	2.5	31
	Divergent	2.61	0.56	1	3.67	2.67	25

Table 4: Probing Depth, continued

Surface	Treatment	Mean	SD	Min	Max	Median	N
6 Months							
MB	Concave	2.82	0.84	2	6	3	30
	Divergent	2.56	0.65	1	4	3	25
MIDB	Concave	1.57	0.57	1	3	2	30
	Divergent	1.78	0.65	1	3	2	25
DB	Concave	2.83	0.65	2	4	3	30
	Divergent	2.68	0.75	1	4	3	25
ML	Concave	2.87	0.78	1	5	3	30
	Divergent	2.92	0.49	2	4	3	25
MIDL	Concave	2.03	0.67	1	3	2	30
	Divergent	2.08	0.57	1	3	2	25
DL	Concave	3	0.83	1	5	3	30
	Divergent	3.08	0.7	2	4	3	25
Average	Concave	2.52	0.46	1.67	3.5	2.5	30
	Divergent	2.52	0.38	1.83	3.17	2.5	25
12 Months							
MB	Concave	2.8	0.72	2	5	3	28
	Divergent	2.76	0.97	2	6	3	25
MIDB	Concave	1.54	0.58	1	3	1.5	28
	Divergent	1.84	0.69	1	4	2	25
DB	Concave	2.89	0.82	2	6	3	28
	Divergent	2.96	0.61	2	4	3	25
ML	Concave	2.96	0.79	2	5	3	28
	Divergent	3.2	0.87	2	5	3	25
MIDL	Concave	2	0.61	1	3	2	28
	Divergent	2.12	0.88	1	5	2	25
DL	Concave	3.11	0.88	2	6	3	28
	Divergent	3.16	0.69	2	5	3	25
Average	Concave	2.55	0.5	1.67	4	2.54	28
	Divergent	2.67	0.54	1.67	4	2.83	25

[figure not shown]

Table 5: Bleeding on Probing

Surface	Time	Concave	Divergent
MB	1 Month	25.81%	29.63%
	3 Months	22.58%	11.11%
	6 Months	19.35%	11.11%
	12 Months	22.58%	18.52%
MIDB	1 Month	25.81%	29.63%
	3 Months	6.452%	25.93%
	6 Months	22.58%	18.52%
	12 Months	29.03%	22.22%
DB	1 Month	9.677%	14.81%
	3 Months	6.452%	22.22%
	6 Months	12.9%	14.81%
	12 Months	25.81%	22.22%
ML	1 Month	25.81%	29.63%
	3 Months	35.48%	22.22%
	6 Months	12.9%	14.81%
	12 Months	19.35%	33.33%
MIDL	1 Month	9.677%	14.81%
	3 Months	12.9%	7.407%
	6 Months	22.58%	14.81%
	12 Months	29.03%	14.81%
DL	1 Month	12.9%	29.63%
	3 Months	19.35%	22.22%
	6 Months	19.35%	25.93%
	12 Months	35.48%	37.04%

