## Bleeding on Probing by Surface

[figure not shown]

Table 6: Number of Surfaces with Bleeding on Probing

Treatment	Mean	SD	Min	Max	Median	N
1 Month						
Concave	1.097	1.2478	0	6	1	31
Divergent	1.482	1.5285	0	5	1	27
3 Months						
Concave	1.032	1.0160	0	4	1	31
Divergent	1.111	1.3960	0	5	1	27
6 Months						
Concave	1.097	1.1932	0	5	1	31
Divergent	1.000	0.9608	0	3	1	27
12 Months						
Concave	1.613	1.4532	0	6	1	31
Divergent	1.482	1.3118	0	5	1	27

Average Number of Surfaces with Bleeding on Probing

[figure not shown]

Table 7: Plaque Index

Surface	Treatment	Mean	SD	Min	Max	Median	N
1 Month							
MB	Concave	0.26	0.63	0	3	0	31
	Divergent	0.41	0.75	0	3	0	27
MIDB	Concave	0.15	0.46	0	2	0	27
	Divergent	0.14	0.47	0	2	0	22
DB	Concave	0.33	0.66	0	3	0	30
	Divergent	0.44	0.75	0	2	0	27
ML	Concave	0.39	0.72	0	3	0	31
	Divergent	0.44	0.89	0	4	0	27
MIDL	Concave	0.11	0.32	0	1	0	27
	Divergent	0.32	0.78	0	3	0	22
DL	Concave	0.52	0.72	0	3	0	31
	Divergent	0.48	0.8	0	3	0	27
Average	Concave	0.29	0.51	0	2.5	0	31
	Divergent	0.36	0.67	0	2.67	0	27
3 Months							
MB	Concave	0.26	0.58	0	2	0	31
	Divergent	0.36	0.76	0	3	0	25
MIDB	Concave	0.11	0.32	0	1	0	27
	Divergent	0.14	0.35	0	1	0	22
DB	Concave	0.23	0.56	0	2	0	31
	Divergent	0.44	0.87	0	3	0	25
ML	Concave	0.23	0.56	0	2	0	31
	Divergent	0.4	0.76	0	3	0	25
MIDL	Concave	0.07	0.27	0	1	0	27
	Divergent	0.18	0.39	0	1	0	22
DL	Concave	0.32	0.6	0	2	0	31
	Divergent	0.48	0.82	0	3	0	25
Average	Concave	0.22	0.46	0	2	0	31
	Divergent	0.33	0.6	0	2.33	0	25

Table 8: Plaque Index, continued

Surface	Treatment	Mean	SD	Min	Max	Median	N
6 Months							
MB	Concave	0.4	0.67	0	3	0	30
	Divergent	0.2	0.41	0	1	0	25
MIDB	Concave	0.1	0.31	0	1	0	30
	Divergent	0	0	0	0	0	25
DB	Concave	0.33	0.66	0	3	0	30
	Divergent	0.36	0.49	0	1	0	25
ML	Concave	0.4	0.72	0	3	0	30
	Divergent	0.24	0.44	0	1	0	25
MIDL	Concave	0.2	0.41	0	1	0	30
	Divergent	0.04	0.2	0	1	0	25
DL	Concave	0.4	0.56	0	2	0	30
	Divergent	0.44	0.51	0	1	0	25
Average	Concave	0.31	0.49	0	2	0	30
	Divergent	0.21	0.26	0	0.67	0	25
12 Months							
MB	Concave	0.56	0.58	0	2	1	27
	Divergent	0.48	0.92	0	4	0	25
MIDB	Concave	0.19	0.4	0	1	0	27
	Divergent	0.28	0.54	0	2	0	25

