DB	Concave	0.74	0.71	0	3	1	27
	Divergent	0.56	0.77	0	3	0	25
ML	Concave	0.85	0.72	0	2	1	27
	Divergent	0.52	0.77	0	3	0	25
MIDL	Concave	0.26	0.45	0	1	0	27
	Divergent	0.2	0.41	0	1	0	25
DL	Concave	0.85	0.72	0	2	1	27
	Divergent	0.68	0.8	0	3	1	25
Average	Concave	0.57	0.48	0	1.67	0.67	27
	Divergent	0.45	0.62	0	2.67	0.33	25

[figure not shown]
Table 9: Gingival Index

Surface	Treatment	Mean	SD	Min	Max	Median	N
1 Month							
MB	Concave	0.52	0.57	0	2	0	31
	Divergent	0.74	0.76	0	2	1	27
MIDB	Concave	0.7	0.67	0	3	1	27
	Divergent	0.77	0.81	0	2	1	22
DB	Concave	0.55	0.62	0	2	0	31
	Divergent	0.7	0.72	0	2	1	27
ML	Concave	0.55	0.62	0	2	0	31
	Divergent	0.81	0.79	0	2	1	27
MIDL	Concave	0.56	0.58	0	2	1	27
	Divergent	0.73	0.55	0	2	1	22
DL	Concave	0.61	0.62	0	2	1	31
	Divergent	0.78	0.75	0	2	1	27
Average	Concave	0.59	0.47	0	2	0.5	31
	Divergent	0.74	0.63	0	2	0.67	27
3 Months							
MB	Concave	0.68	0.75	0	3	1	31
	Divergent	0.58	0.78	0	2	0	24
MIDB	Concave	0.59	0.57	0	2	1	27
	Divergent	0.64	0.79	0	2	0	22
DB	Concave	0.48	0.63	0	2	0	31
	Divergent	0.6	0.71	0	2	0	25
ML	Concave	0.74	0.63	0	2	1	31
	Divergent	1	0.76	0	2	1	25
MIDL	Concave	0.59	0.57	0	2	1	27
	Divergent	0.68	0.78	0	2	0.5	22
DL	Concave	0.87	0.63	0	2	1	30
	Divergent	0.96	0.79	0	2	1	25
Average	Concave	0.65	0.47	0	2	0.67	31
	Divergent	0.74	0.66	0	2	0.5	25

Table 10: Gingival Index, continued

Surface	Treatment	Mean	SD	Min	Max	Median	N
6 Months							
MB	Concave	0.67	0.61	0	2	1	30
	Divergent	0.52	0.71	0	2	0	25
MIDB	Concave	0.53	0.63	0	2	0	30
	Divergent	0.68	0.69	0	2	1	25
DB	Concave	0.7	0.6	0	2	1	30
	Divergent	0.68	0.63	0	2	1	25
ML	Concave	0.83	0.75	0	2	1	30
	Divergent	0.96	0.61	0	2	1	25
MIDL	Concave	0.6	0.62	0	2	1	30
	Divergent	0.68	0.56	0	2	1	25
DL	Concave	0.83	0.59	0	2	1	30
	Divergent	0.92	0.57	0	2	1	25
Average	Concave	0.69	0.47	0	1.83	0.67	30
	Divergent	0.74	0.43	0	1.67	0.67	25
12 Months							
MB	Concave	0.71	0.76	0	2	1	28
	Divergent	0.74	0.69	0	2	1	23
MIDB	Concave	0.71	0.6	0	2	1	28
	Divergent	0.65	0.71	0	2	1	23
DB	Concave	1.04	0.79	0	3	1	28
	Divergent	0.87	0.63	0	2	1	23
ML	Concave	1.04	0.79	0	3	1	28
	Divergent	1.04	0.77	0	2	1	23
MIDL	Concave	0.82	0.61	0	2	1	28

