### Average Keratinized Mucosa Width

### Statistical Analyses

We used mixed models to analyze the effect of time and treatment on each of the variables of interest. The results are summarized in tables below.

Canfield values, bleeding on probing, plaque index, gingival index, and keratinized mucosa width changed significantly over time. Canfield values, bleeding on probing, plaque index, and keratinized mucosa width have a curved relationship with time. Treatment alone is not significant in any model, but is significant in

an interaction with time in bucco-lingual thickness; the effect of treatment on this measure is significantly different across time points.

Table 13: Canfield Model

	P-Value
Time	< .001
Time 	< .001
Treatment	0.853

Table 14: Probing Depth Model

	P-Value
Time	0.096
Treatment	0.307

Table 15: Bleeding on Probing Model

	P-Value
Time	0.0791
Time 	0.0282
Treatment	0.9170

Table 16: Plaque Index Model

	P-Value
Time	0.1640
Time 	0.0436
Treatment	0.9880

Table 17: Gingival Index Model

	P-Value
Time	0.00146
Treatment	0.40900

Table 18: Bucco-Lingual Thickness Model

	P-Value
Time	0.0744
Time 	0.1440
Treatment	0.6740
Treatment:Time	0.0169
Treatment:Time 	0.0359

Table 19: Keratinized Mucosa Width Model

	P-Value
Time	< .001
Time 	< .001
Treatment	0.106

Over time, there was not a significant relationship between bucco-lingual thickness and any of Canfield values, probing depth, bleeding on probing, or keratinized mucosa.

Table 20: Canfield and Bucco-Lingual Thickness

	P-Value
Time	< .001
Time 	< .001
Thickness	0.178

Table 21: Probing Depth and Bucco-Lingual Thickness

	P-Value
Time	0.0928
Thickness	0.6720

Table 22: Bleeding on Probing and Bucco-Lingual Thickness

	P-Value
Time	0.1190
Time 	0.0381
Thickness	0.7340

Table 23: Keratinized Mucosa Width and Bucco-Lingual Thickness

	P-Value
Time	< .001
Time 	< .001
Thickness	0.705

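### Average probing depth has a different site mix at 1 and 3 months than later, so the time slope behind p = 0.096 is understated if Table 14 models that average, or single sites without a site term

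*Combined protocol and SAP*

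**What the plan says.** The secondary objective in Study objectives is to "Evaluate changes in peri-implant health indicators, such as Gingival Index (GI), Probing Pocket Depth (PPD), and Bleeding on Probing (BOP". Outcome variables specifies "probing pocket depths (PPD) at six sites (disto-lingual, mesio-lingual, mid-lingual, mesio-buccal, disto-buccal, mid-buccal".

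The statistical report dated October 1, 2019 says of incomplete records: "We did keep subjects with partial data in at least one of the variables". It gives no rule for averaging over a subject's missing sites. Its Statistical Analyses section says: "We used mixed models to analyze the effect of time and treatment on each of the variables of interest". Table 14 (probing depth) lists Time (p = 0.096) and Treatment (p = 0.307). Table 21 lists Time (p = 0.0928) and Thickness (p = 0.672). The report does not say whether the response is the subject average or the single-site reading, or whether a site term was fitted.

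**The concern.** A subject average over whichever sites were probed is comparable across visits only if the same sites are probed each time. Here the shallow mid-buccal and mid-lingual sites are missing for some subjects at the first two visits and for none at the last two. That raises the early averages and flattens the rise over time.

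The report lists the gingival index and bleeding on probing as changing significantly over time. Probing depth is the only one of the three indicators named in the objective that is not listed. If the model used the average, or pooled single sites without a site term, part of that null result comes from which sites were measured. In addition, one printed Average row cannot be right, whatever Table 14 modelled.

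**Working it through.** **Inputs.** Site means, site N and Average rows come from Table 3 (1 and 3 months) and Table 4 (6 and 12 months). Proximal sites are MB, DB, ML and DL; mid sites are MIDB and MIDL. The counts assume that the same subjects lack both mid sites, whose N are equal at each visit.

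**Step 1: who is averaged without mid sites.** At 1 month, (31 − 27) + (27 − 22) = 9 of 58. At 3 months, (31 − 27) + (25 − 22) = 7 of 56. At 6 and 12 months every site has the same N (30/25 and 28/25).

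**Step 2: which averaging rule reproduces the printed rows.**
- Equal-site mean = sum of the six site means / 6.
- Available-site mean = [n_mid × equal-site mean + (n_prox − n_mid) × proximal mean] / n_prox. This takes the four-site subjects' proximal depths as typical.

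Example, concave at 1 month: proximal mean (2.68 + 2.58 + 2.81 + 2.84)/4 = 2.7275; mid mean (1.50 + 1.89)/2 = 1.695; equal-site mean (4 × 2.7275 + 2 × 1.695)/6 = 2.383; available-site mean (27 × 2.383 + 4 × 2.7275)/31 = 2.428.

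| Visit, arm | Proximal | Mid | Equal-site | Available-site | Printed |
|---|---|---|---|---|---|
| 1 m concave | 2.728 | 1.695 | 2.383 | 2.428 | 2.42 |
| 1 m divergent | 2.795 | 1.840 | 2.477 | 2.536 | 2.53 |
| 3 m concave | 2.760 | 1.740 | 2.420 | 2.464 | 2.47 |
| 3 m divergent | 2.915 | 1.965 | 2.598 | 2.636 | 2.61 |
| 6 m concave | 2.880 | 1.800 | 2.520 | 2.520 | 2.52 |
| 6 m divergent | 2.810 | 1.930 | 2.517 | 2.517 | 2.52 |
| 12 m concave | 2.940 | 1.770 | 2.550 | 2.550 | 2.55 |
| 12 m divergent | 3.020 | 1.980 | 2.673 | 2.673 | 2.67 |

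Mid sites are 0.88–1.17 mm shallower in every arm and visit. Only the first four rows can separate the rules. Three of them match available-site averaging within 0.01 and miss equal-site averaging by 0.04–0.05. The fourth matches neither.

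The Divergent 1-month Average maximum of 3.25 points the same way. Six whole-millimetre readings cannot give it (19/6 = 3.17, 20/6 = 3.33), but four can (13/4). Mean × N at that visit gives whole totals at all six sites (71, 40, 77, 77, 41, 77).

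**Step 3: the Divergent 3-month Average row.** All four proximal sites have N = 25 and minimum 2, and both mid sites have minimum 1. The lowest possible subject average is therefore (4 × 2 + 2 × 1)/6 = 1.67, but the row prints a minimum of 1.

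**Step 4: effect on the time slope.** The fit is an N-weighted line through the eight group means, with one intercept per arm and a common slope.
- Printed averages: 0.0108 mm/month. Equal-site means: 0.0151. Shortfall 1 − 0.0108/0.0151 = 28%.
- Without the faulty row: 0.0120 against 0.0166, also 28%.
- Single sites pooled without a site term: 0.0116, 23% lower than 0.0151.
- Rise from 1 to 12 months (concave/divergent): 0.13/0.14 mm printed, 0.17/0.20 mm equal-site.

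**Step 5: how far this depends on the unmeasured mid sites.**
- If they were 0.3 mm shallower than the measured ones, the shortfall is 35%; if 0.3 or 0.5 mm deeper, 20% or 14%. It is zero only at 0.86 mm deeper.
- Table rounding plus sampling error of the 3–5 unmeasured subjects per cell (20,000 normal draws, printed mid-site SDs, missing at random) gives a widest 95% range of 15–38%.
- In the three usable cells, the printed averages imply how far the four-site subjects' proximal depths differ from the others'. Giving their mid sites the same offsets yields 28–32%.

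**Step 6: what is not affected.** Divergent minus concave, printed against equal-site, is 0.11/0.09, 0.14/0.18 (faulty row), 0.00/0.00 and 0.12/0.12 mm at the four visits. The plaque and gingival indices (Tables 7 and 9) have the same 27/22 shortfall, but their slopes barely move: 0.0189 against 0.0191 for plaque, 0.0222 against 0.0219 for gingival, both under 2%.

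**The case against.** **The response is unknown.** Table 14 is a summary of p-values, and a site-level fit with a site term would be largely free of this problem. That stands, so the effect on p = 0.096 is conditional. It does not touch the site mix of the Average rows or the impossible minimum, both of which follow from the printed tables alone.

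**The 28% is not the bias of the reported model.** It comes from a line through group means, whereas a mixed model weights within-subject change, and some subjects drop out. This also stands as to size. In simulated site-level data fitted with a random-intercept model, the six-site slope exceeded the available-site slope in every run, by a factor of about 1.5–1.6, against 0.0151/0.0108 = 1.40 here. The direction is secure; the exact size is not.

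**Half-millimetre readings exist in these data.** Concave MIDB at 1 month has a median of 1.5 with N = 27, and the Divergent 3-month totals include 38.5 and 76.5. The 3.25 maximum is therefore supporting evidence only. The whole-number totals at that visit mean that a half-millimetre reading there would need a second one at the same site.

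**The 3-month mismatch may be one error, not two.** Raising the impossible minimum from 1 to 1.67 adds 0.67/25 = 0.027 and moves 2.61 to about 2.637, next to the available-site value of 2.636. If so, that row also supports available-site averaging.

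**The stakes are small.** The disputed part of the rise is about 0.04–0.06 mm over 11 months, and the trial's question is the contrast between abutments. This is fair. It limits the importance of the point but does not remove it, because change in probing depth is a stated secondary objective and the correction is cheap.

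**Conclusion.** The concern holds. The Average probing depth changes its site composition between the early and late visits, and the printed rows behave as available-site averages. If Table 14 models that average, the time slope is understated by about 28% (15–38% with rounding and sampling error, assuming missing at random). If it models single sites without a site term, the figure is about 23%. Under the same condition Table 21 is exposed in the same way. The direction would change only if the unmeasured mid sites were more than 0.86 mm deeper than the measured ones.

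No claim is made that time would become significant; that needs the subject data. The Divergent 3-month Average row is wrong as printed whatever was modelled. The change should be made, but it bears on one secondary time result and on no treatment conclusion.

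**What to change.** - Refit both probing-depth models at site level, using every probed site, with a six-level site term and random effects for sites clustered within subject and visit. Keep each table's own terms: Time and Treatment for Table 14, Time and Thickness for Table 21. Report the Time result from this fit in place of p = 0.096. If Table 14 was already such a fit, saying so settles the point.
- State the response modelled and the number of sites per subject and visit.
- A proximal-only analysis may be added as a complete-site check, labelled as a different quantity. From the tables the slope is 0.0187 mm/month at proximal sites and 0.0079 at mid sites.
- Check and correct the Divergent 3-month Average row.
- Apply the same check to the plaque and gingival index averages, where the tables suggest little effect.

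Cost: two secondary models rerun on existing data, one table row checked, and two further averages checked.
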